The Effects of Music and Auditory Beat Stimulation on Anxiety Study Protocol

Approved by the Ryerson Ethics Board: REB 2020-068 on March 26th, 2020, renewal
approval: March 18th, 2021

NCT#:

Date: 2021-11-26

Study Protocol

Participants

Participants (n=318) who are taking anti-anxiety medication will be recruited from Prolific, an online research recruitment platform. A power analysis was conducted drawing effect sizes from a previous study that examined how anxiety levels (measured by the STAI), were affected under the following experimental conditions: binaural beats, music with binaural beats and no-intervention (Padmanabhan et al., 2005). The power analysis indicated that to achieve a power of 0.80 at a significance of $p = 0.05$, a minimum of 45 participants in each treatment group are required (Padmanabhan et al., 2005). An additional 10 participants will be recruited to account for potential participant attrition. Participants will be pre-screened for moderate to severe anxiety using the STICSA trait questionnaire (Grös, Antony, Simms, & McCabe, 2007). Participants will then be randomly assigned to one treatment arm.

Experimental treatment conditions

Each of the experimental treatment conditions below will be 24 minutes in duration, as this seems to be the exposure time needed for binaural beats to reduce anxiety levels and for general effectiveness of binaural beats in other areas such as cognition (Garcia-Argibay, 2019; Isik et al., 2017).

1. Pink noise (control condition)
2. Theta ABS
3. Theta ABS with music generated by LUCID's calm mode
4. Music generated by LUCID's calm mode

Procedure

After reading and signing the consent form and going over experimental expectations, participants will be asked to fill out the Short Test of Music Preferences (STOMP), Queen's Music Questionnaire, the Positive and Negative Affect Scale (PANAS), Self-Assessment Manikin (SAM), Eysenck Personality Questionnaire and the STICSA state version. Participants will then undergo their respective listening condition. After undergoing experimental treatment, participants will complete the following questionnaires: STICSA state version, SAM and the PANAS.

Outcome measures and questionnaires

Participants show a more pleasurable emotional response to their own preferred music compared to experimenter-selected music (Davis & Thaut, 1989; Thaut & Davis, 1993). We therefore decided to incorporate the Short Test of Music Preferences (STOMP) as a covariate in our analyses (Rentfrow & Gosling, 2003). The Queen's Music Questionnaire will be administered to assess musical education and daily music exposure of each participant, which will be used as a covariate in our analyses. The Eysenck Personality Questionnaire will be used to determine participants' extraversion and introversion (Rocklin & Revelle, 1981). The State Trait Inventory for Cognitive and Somatic Anxiety (STICSA) will be used to pre-screen high trait anxiety participants (trait version) for participation in this study (Grös et al., 2007).

The state version of STICSA will be used to assess state anxiety before and after experimental treatment. This will serve as the primary outcome measure. The Positive and Negative Affect Scale (PANAS) will be used to assess mood (Watson, Clark, & Tellegen, 1988) before and after experimental treatment. The Self-Assessment Manikin (SAM)

questionnaire will be used to assess valence and arousal of the participant before and after experimental treatment (Bradley & Lang, 1994).

References

Bradley, M. M., & Lang, P. J. (1994). Measuring emotion: The self-assessment manikin and the semantic differential. *Journal of Behavior Therapy and Experimental Psychiatry*, 25(1), 49-59. doi:[https://doi.org/10.1016/0005-7916\(94\)90063-9](https://doi.org/10.1016/0005-7916(94)90063-9)

Davis, W. B., & Thaut, M. H. (1989). The Influence of Preferred Relaxing Music on Measures of State Anxiety, Relaxation, and Physiological Responses. *Journal of Music Therapy*, 26(4), 168-187. doi:10.1093/jmt/26.4.168

Garcia-Argibay, M. (2019). Efficacy of binaural auditory beats in cognition, anxiety, and pain perception: a meta-analysis. *Psychological Research*, 83(2), 357-372. doi:10.1007/s00426-018-1066-8

Grös, D. F., Antony, M. M., Simms, L. J., & McCabe, R. E. (2007). Psychometric properties of the State-Trait Inventory for Cognitive and Somatic Anxiety (STICSA): Comparison to the State-Trait Anxiety Inventory (STAI). *Psychological assessment*, 19(4), 369.

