**The Effects of Music and Auditory Beat Stimulation on Anxiety
Statistical Analysis Plan**

Approved by the Ryerson Ethics Board: REB 2020-068 on March 26th, 2020, renewal
approval: March 18th, 2021

NCT#:

Date: 2021-11-26

Statistical Analysis Plan

For each participant the post-experimental treatment STICSA, PANAS and SAM Valence and arousal scores will be subtracted from the pre-experimental treatment scores. Shapiro-Wilks normality and homogeneity of variances tests will be done on the STICSA, PANAS and SAM datasets, and homogeneity of covariances tests will be done on music preferences, and personality type datasets to determine if assumptions of the Multivariate Analysis of Covariance (MANCOVA) are satisfied. If these assumptions are satisfied, a MANCOVA over the factor of experimental condition will be performed with music preferences, spontaneous blink rate and personality type as covariates and the relative differences (Pre-treatment – Post-treatment) of STICSA, PANAS and SAM Valence and arousal scores as dependent variables. Post-hoc Tukey's HSD multiple comparisons tests will be done comparing the LUCID music with theta ABS condition with all of the other experimental conditions. Further post-hoc Tukey's HSD multiple comparisons tests will be done comparing the theta ABS and LUCID music conditions with the pink noise condition. Statistically accounting for music preferences, spontaneous blink rate, personality type, age and gender as covariates should reduce some variability in the analysis.

If the data do not satisfy the assumptions for the MANCOVA, permutations tests, specifically the ImPerm package in R will be used to conduct a permutation version of the repeated measures ANCOVA for each dependent variable (STICSA Somatic, STICSA Cognitive, Positive Affect (PANAS), Negative Affect (PANAS) and SAM Valence and arousal scores), with time (pre and post intervention) as the within subjects variable and experimental condition as the between subjects factor. Post-hoc permutation tests will be done comparing the LUCID music with theta binaural beats condition with all of the other experimental conditions for each dependent variable. Permutation tests are a good way to control the type I error rate for multiple comparisons, it is non-parametric and so makes no assumptions about the underlying distribution of the data that are common in other inferential statistical tests (Camargo, Azuaje, Wang, & Zheng, 2008; Good, 1994; Kuehl, 2000).

References

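### The stated 0.80 power at 45 per arm is not supported for four of the SAP's five planned contrasts, including all three against pink noise

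*Protocol*

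**What the plan says.** The Participants section of the protocol gives the basis of the sample size: "A power analysis was conducted drawing effect sizes from a previous study". It describes that study's conditions as "binaural beats, music with binaural beats and no-intervention" and concludes that "a minimum of 45 participants in each treatment group are required" for power 0.80 at a significance level of 0.05. It gives no effect size, standard deviation, test, sidedness or source contrast. The same section opens with a total of 318 participants and does not connect that total to the 45.

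Under Experimental treatment conditions, the protocol lists four arms: pink noise, theta ABS, theta ABS with LUCID music, and LUCID music alone. The first is labelled "Pink noise (control condition". The control lasts as long as the other arms: "Each of the experimental treatment conditions below will be 24 minutes in duration".

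If the MANCOVA assumptions hold, the SAP plans Tukey HSD comparisons of the combination arm with each of the other three arms, and further ones "comparing the theta ABS and LUCID music conditions with the pink noise condition". That makes five named contrasts, three of them against pink noise.

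**The concern.** A power figure belongs to a particular contrast with a particular assumed effect. As the protocol describes it, the sizing study had no pink-noise arm and no music-only arm, so no effect drawn from it can be an effect against either. Neither document gives a reason for treating pink noise as equivalent to no intervention, and neither discounts the effect for the change of control.

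The change could matter. A difference from no intervention can include whatever comes from resting, listening to something and expecting benefit. A sound control of equal length may share part of that, which would leave a smaller difference to detect.

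The interpretation of results is at stake. The 0.80 is the only power figure in either document, so a reader who meets a non-significant pink-noise contrast has nothing else to judge it by and may take it as a null from a comparison with 80% power.

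**Working it through.** **1. Which contrasts the sizing study could inform.**

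| SAP contrast | Both arms in the sizing study as described? |
|---|---|
| Combination vs theta ABS | Yes |
| Combination vs music | No (music alone absent) |
| Combination vs pink noise | No (pink noise absent) |
| Theta ABS vs pink noise | No (pink noise absent) |
| Music vs pink noise | No (both absent) |

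Four of the five have no counterpart.

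**2. What the 45 implies.** The 45 cannot be reproduced forward because no effect size is given, so I solved backward. Inputs from Participants: n = 45 per arm, power 0.80, alpha 0.05. Assumptions: two-sided test, two-group comparison of means.

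- Normal approximation: d = (1.960 + 0.842) × √(2/45) = 2.802 × 0.2108 = 0.591.
- Noncentral t with 88 degrees of freedom: d = 0.597, used below.
- If one-sided: d = 0.524 (normal) or 0.528 (t).
- If an omnibus F test: f = 0.270 with three groups, 0.249 with four. Going the other way, a four-group ANOVA with f = 0.25 needs 44.6, so 45 per group. The protocol does not say this was the route.

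**3. Arm sizes.** Taking 45 as the arm size gives 4 × 45 = 180 in total. The stated total gives 318/4 = 79.5, so about 79 per arm if the split is equal; the allocation ratio is not stated. The 10 added for attrition do not bridge the gap: 180 + 10 = 190, or 4 × 55 = 220 if the 10 are per arm.

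**4. Power if pink noise absorbs part of the effect.** The share absorbed, s, is unknown, so this is a sensitivity range. The noncentrality is (1 − s) × 0.597 × √(n/2). For the unadjusted test the critical value is that of a two-sided t. For Tukey HSD with four groups it is the studentized range quantile divided by √2 with 4(n − 1) degrees of freedom: 3.668/√2 = 2.594 at n = 45 and 3.653/√2 = 2.583 at n = 79.

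| Absorbed | d | n = 45, unadjusted | n = 45, Tukey | n = 79, unadjusted | n = 79, Tukey |
|---|---|---|---|---|---|
| 0% | 0.597 | 0.80 | 0.60 | 0.96 | 0.88 |
| 10% | 0.537 | 0.71 | 0.48 | 0.92 | 0.79 |
| 20% | 0.478 | 0.61 | 0.37 | 0.85 | 0.66 |
| 30% | 0.418 | 0.50 | 0.27 | 0.74 | 0.52 |
| 50% | 0.299 | 0.29 | 0.12 | 0.46 | 0.24 |

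At 79 per arm the unadjusted test keeps 0.80 until about 25% is absorbed (d = 0.449; 0.449/0.597 = 0.75). Tukey power at that point is 0.59.

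If the 45 came from an omnibus F test, the same four discounts at 45 per arm give 0.71, 0.60, 0.48 and 0.27 (three groups) or 0.70, 0.59, 0.47 and 0.25 (four groups), close to the unadjusted column.

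**5. Detectable difference at 0.80 power.** This needs no assumption about absorption.

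| Per arm | Unadjusted d | Tukey d |
|---|---|---|
| 45 | 0.60 | 0.73 |
| 79 | 0.45 | 0.55 |

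No allowance is made for any gain from covariates.

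**The case against.** Three objections have force.

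First, a reader might infer that the 0.80 describes an effect against no intervention, and so a comparison this trial never makes. The protocol does not say that. It refers to effect sizes in the plural from a three-condition study and does not name the contrast. The figure may belong to combination versus ABS, which this trial does make, or to an omnibus test, which would match the SAP's opening MANCOVA. This stands, and it limits the point to the contrasts with no counterpart in the source.

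Second, a reader might infer that power must fall well below 0.80. Neither document says what pink noise does to anxiety, so the direction of the change is a plausible assumption and its size is unknown. The 45 is also called a minimum. With 318 split equally, unadjusted power is 0.92 at 10% absorbed and 0.85 at 20%. The documents therefore do not show that the trial is underpowered. This stands too, with two limits: 318 is not tied to the 45 or presented as an allowance for the control, and the planned tests are Tukey tests, for which the margin is thinner.

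Third, replacing the 0.80 with unadjusted detectable differences of 0.60 or 0.45 would repeat the fault. Under Tukey HSD those effects have power of only about 0.60 (45 per arm) and 0.59 (79 per arm). This is right, so the replacement has to be worked out for the planned test.

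The SAP also expects covariates to reduce variability, which could recover some power. The documents do not quantify this.

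**Conclusion.** The point holds in a limited form. The 0.80 at 45 per arm is unsupported for the three pink-noise contrasts and for combination versus music, because the sizing study as described contains neither pink noise nor music alone. This rests on the documents alone.

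The size of any shortfall is conditional. It assumes the implied d of 0.597, a two-sided 0.05 test, equal arms and an absorbed share between 10% and 50%. The Tukey figures also assume a four-group family with pooled variance and apply to the MANCOVA route, not to the SAP's permutation fallback. Even with nothing absorbed, Tukey power at d = 0.597 is about 0.60 at 45 per arm and 0.88 at 79. Pink noise is not shown to be a poor control. What is missing is a power statement that fits the contrasts planned against it.

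**What to change.** In Participants:

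- Name the source contrast, effect size and test that gave 45.
- Stop attaching 0.80 to the pink-noise contrasts.
- State instead the smallest standardised difference against pink noise detectable with 0.80 power at the actual arm size under Tukey HSD: about d = 0.73 at 45 per arm, or about d = 0.55 at about 79 per arm if 318 is split equally (two-sided 0.05, before any covariate gain). The unadjusted 0.60 and 0.45 can be shown alongside, labelled as such.
- Give the 10-50% sensitivity table, with the absorbed share marked as an assumption.

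In the SAP, add one sentence: a non-significant pink-noise contrast is read from its confidence interval against that detectable difference, not as evidence of no effect.

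The cost is a rewritten sample-size paragraph, a short table and that sentence. The stated power becomes less favourable. Arms and recruitment do not change.

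### The STICSA trait score is available before randomisation but is left out of both analyses; adding it as a continuous covariate is a low-cost gain in precision

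*Protocol*

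**What the plan says.** **Screening.** The Participants section of the Protocol says "Participants will be pre-screened for moderate to severe anxiety using the STICSA trait questionnaire". The next sentence is "Participants will then be randomly assigned to one treatment arm", so the trait score precedes assignment. The section on outcome measures says that the STICSA "will be used to pre-screen high trait anxiety participants (trait version) for participation in this study". Neither place gives a cut-off, or says whether a total or a subscale score decides entry. A second entry condition is clear: participants are people "who are taking anti-anxiety medication will be recruited from Prolific, an online research recruitment platform".

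**Primary outcome.** The same Protocol section makes the state version of the STICSA, before and after the session, the primary outcome measure.

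**Covariates.** The first paragraph of the SAP specifies a MANCOVA of pre-minus-post differences "with music preferences, spontaneous blink rate and personality type as covariates". That paragraph ends with a longer list and its purpose: "Statistically accounting for music preferences, spontaneous blink rate, personality type, age and gender as covariates should reduce some variability in the analysis". The Protocol also names the Queen's Music Questionnaire as a covariate. The personality measure is not a measure of trait anxiety: "The Eysenck Personality Questionnaire will be used to determine participants' extraversion and introversion".

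**Fallback.** The second paragraph of the SAP describes a permutation repeated measures ANCOVA "with time (pre and post intervention) as the within subjects variable and experimental condition as the between subjects factor". It names no covariate for that model.

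**The concern.** Covariates serve precision best when they predict the outcome. The plan adjusts for music preference, personality type and blink rate, and mentions age and gender. It omits the one baseline variable that comes from the same inventory as the primary outcome, although that variable is collected before assignment and needs no further questionnaire.

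What is at stake is the width of the confidence intervals for the STICSA comparisons, and protection against a chance difference between arms in trait anxiety. The reader of the results should also be able to see how anxious the enrolled sample was. At present the two descriptions of the screen do not settle that, because neither is tied to a score.

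**Working it through.** **Where the score appears**

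| Place | Terms named | Trait STICSA? |
|---|---|---|
| Protocol, random assignment | none | no |
| Protocol, planned covariates | STOMP, Queen's Music Questionnaire | no |
| SAP, MANCOVA | music preferences, blink rate, personality type | no |
| SAP, longer list | the same, plus age and gender | no |
| SAP, fallback model | time, condition | no |

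**Inputs.** From the Protocol: 45 per group as a minimum, power 0.80, significance level 0.05, total 318. Assumed: a two-sided test, outcome SD = 1, equal allocation (318/4 = 79.5, taken as 79), and a correlation *r* between trait score and change in state STICSA of 0.2 to 0.5. The documents give no value of *r*.

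**The plan's figure of 45.** No effect size is stated, so 45 cannot be reproduced directly. Solved backwards for two arms:

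d = √(2/45) × (1.960 + 0.842) = 0.2108 × 2.802 = 0.591.

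A t-test calculation gives 0.597, and a one-sided test 0.524. The implied effect is thus about 0.6 SD, and 0.591 is used below.

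**Effect of adjustment.** A covariate with correlation *r* lowers the residual variance to 1 − r², so

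power = Φ( d / [√(1 − r²) × √(2/n)] − 1.960 ).

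Worked case, r = 0.5, n = 45: 0.591 / (0.866 × 0.2108) = 3.24; 3.24 − 1.96 = 1.28; power 0.90.

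| r | 1 − r² | n per arm for the same power, 45 × (1 − r²), rounded up | Power at 45 | Power at 79 |
|---|---|---|---|---|
| 0 | 1.00 | 45 | 0.80 | 0.96 |
| 0.1 | 0.99 | 45 | 0.80 | 0.96 |
| 0.2 | 0.96 | 44 | 0.82 | 0.97 |
| 0.3 | 0.91 | 41 | 0.84 | 0.97 |
| 0.4 | 0.84 | 38 | 0.86 | 0.98 |
| 0.5 | 0.75 | 34 | 0.90 | 0.99 |

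These figures are for one pairwise contrast on STICSA change, with no multiplicity adjustment. They ignore the covariates already planned, so *r* is best read as the correlation that remains after those.

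**Chance imbalance.** The difference in mean trait score between two arms has standard error √(2/n) in SD units: 0.211 at 45 and 0.159 at 79. The probability that a given pair differs by more than 0.25 SD is 0.24 and 0.12 respectively. A gap of 0.25 SD moves the unadjusted contrast by 0.25r, or 0.05 to 0.125 SD for r of 0.2 to 0.5.

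**Condition-by-trait interaction.** With two equal severity groups (assumed), the standard error of the difference in effects is √(8/n). For a difference of 0.591 SD, power is Φ(0.591/0.422 − 1.960) = 0.29 at 45 per arm and Φ(0.591/0.318 − 1.960) = 0.46 at 79.

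**The case against.** The strongest case is that adjustment is optional. Unstratified randomisation gives a valid test, and chance imbalance is already reflected in the standard error. The outcome is a within-person difference, which removes part of any stable level of anxiety, so trait score may predict change only weakly. Screening on the trait score also narrows its range, which tends to lower the correlation. At r = 0.1 the gain is negligible, and at about 79 per arm power is already 0.96. All of this stands. It limits the size of the gain but does not argue against using a score already in hand.

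A reader might infer more from the text in four ways, and the documents support none of them.

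- *The entry rule contradicts itself.* With no cut-off in either section, high trait anxiety may simply be shorthand for passing the moderate-to-severe screen. The labels differ, but two different thresholds are not shown.
- *The result therefore applies to an undefined mix.* Medication use is a stated criterion. What is unclear about severity comes from the missing cut-off, and not from omitting the score from the model.
- *Randomisation must be stratified by severity.* This is a debatable design preference. Nothing in the documents makes it necessary for a valid comparison.
- *An effect confined to one severity level would be diluted.* Nothing in the documents suggests that the effect varies with trait anxiety. Stratifying would not restore power lost in that way, and the interaction test has power of only 0.29 to 0.46 in the case worked above.

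**Conclusion.** The point holds as a missed gain in precision. The trait score is collected before assignment, is closely related to the primary outcome by construction, and is absent from every covariate list and from the fallback model. No bias in the planned comparison is shown.

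The size depends on an assumed correlation of 0.2 to 0.5: 2 to 10 percentage points of power at 45 per arm, and 1 to 3 points at about 79 per arm. The second figure assumes that the 318 are allocated equally, which the Protocol does not state. If the correlation is nearer 0.1, the gain is close to nil.

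The different labels for the screen, without a cut-off, are a secondary matter of clarity.

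**What to change.** 1. In the SAP, name the continuous STICSA trait score as a pre-specified covariate for the STICSA state outcome on both paths. In the MANCOVA it joins the existing covariates. In the fallback, it should enter with a trait-by-time term, because with pre and post scores a trait main effect alone does not adjust the change.
2. State which trait score is used (total or subscale), and report its distribution by arm.
3. In the Protocol, reconcile the Participants and outcome-measures sections to one trait criterion, with the score and cut-off that the investigators actually apply.
4. A condition-by-trait interaction is optional. If included, label it exploratory and report estimates with confidence intervals.

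The cost is one degree of freedom in the MANCOVA, two terms in the fallback (trait and trait-by-time) and a few sentences of text. No further questionnaire is needed, provided that the pre-screen scores are kept and linked to the trial records. The covariate should be fixed before outcome data are examined.

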**The Effects of Music and Auditory Beat Stimulation on Anxiety
Statistical Analysis Plan**

Approved by the Ryerson Ethics Board: REB 2020-068 on March 26th, 2020, renewal
approval: March 18th, 2021

NCT#:

Date: 2021-11-26

Statistical Analysis Plan

For each participant the post-experimental treatment STICSA, PANAS and SAM Valence and arousal scores will be subtracted from the pre-experimental treatment scores. Shapiro-Wilks normality and homogeneity of variances tests will be done on the STICSA, PANAS and SAM datasets, and homogeneity of covariances tests will be done on music preferences, and personality type datasets to determine if assumptions of the Multivariate Analysis of Covariance (MANCOVA) are satisfied. If these assumptions are satisfied, a MANCOVA over the factor of experimental condition will be performed with music preferences, spontaneous blink rate and personality type as covariates and the relative differences (Pre-treatment – Post-treatment) of STICSA, PANAS and SAM Valence and arousal scores as dependent variables. Post-hoc Tukey's HSD multiple comparisons tests will be done comparing the LUCID music with theta ABS condition with all of the other experimental conditions. Further post-hoc Tukey's HSD multiple comparisons tests will be done comparing the theta ABS and LUCID music conditions with the pink noise condition. Statistically accounting for music preferences, spontaneous blink rate, personality type, age and gender as covariates should reduce some variability in the analysis.

If the data do not satisfy the assumptions for the MANCOVA, permutations tests, specifically the ImPerm package in R will be used to conduct a permutation version of the repeated measures ANCOVA for each dependent variable (STICSA Somatic, STICSA Cognitive, Positive Affect (PANAS), Negative Affect (PANAS) and SAM Valence and arousal scores), with time (pre and post intervention) as the within subjects variable and experimental condition as the between subjects factor. Post-hoc permutation tests will be done comparing the LUCID music with theta binaural beats condition with all of the other experimental conditions for each dependent variable. Permutation tests are a good way to control the type I error rate for multiple comparisons, it is non-parametric and so makes no assumptions about the underlying distribution of the data that are common in other inferential statistical tests (Camargo, Azuaje, Wang, & Zheng, 2008; Good, 1994; Kuehl, 2000).

References

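### The homogeneity-of-covariances check is applied to pre-listening covariates, so it says nothing about the MANCOVA assumption yet helps choose the analysis; outcome correlations and covariate slopes go unchecked

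*SAP*

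**What the plan says.** The first paragraph of the SAP sets out two groups of pretests. For the outcomes, "Shapiro-Wilks normality and homogeneity of variances tests will be done on the STICSA, PANAS and SAM datasets". For two other variables, "homogeneity of covariances tests will be done on music preferences, and personality type datasets". Both groups are run "to determine if assumptions of the Multivariate Analysis of Covariance (MANCOVA) are satisfied".

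The next sentence fixes the role of each variable. The model is fitted "with music preferences, spontaneous blink rate and personality type as covariates", and takes the pre-minus-post differences "of STICSA, PANAS and SAM Valence and arousal scores as dependent variables". Music preferences and personality type are therefore covariates, not outcomes.

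The second paragraph makes the pretests a decision rule: "If the data do not satisfy the assumptions for the MANCOVA, permutations tests, specifically the ImPerm package in R will be used", with a separate repeated-measures analysis for each of six outcomes. The SAP names neither the covariance test nor the significance level for any pretest.

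The Protocol (Participants, Procedure) randomises participants to four conditions and has them complete the music-preference and personality questionnaires before listening. Under Outcome measures and questionnaires it justifies the music-preference covariate thus: "Participants show a more pleasurable emotional response to their own preferred music compared to experimenter-selected music".

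**The concern.** MANCOVA assumes that the covariance matrix of the dependent variables, given the covariates, is the same in every arm. The usual adjusted model also assumes that each covariate has the same slope in every arm. Checking either assumption requires the dependent variables, and the planned covariance test does not use them.

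Because the two covariates are recorded before exposure in randomised arms, their covariance matrices are equal across arms by design. A rejection is a chance event or a reaction to non-normal questionnaire scores. A pass carries no information about the outcomes.

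The result matters because it feeds the choice of analysis, and the two routes differ. The MANCOVA route includes post-hoc comparisons of the combined arm with every other arm, and of theta ABS alone and music alone with pink noise. The fallback lists only comparisons with the combined arm. A diversion therefore drops two planned comparisons with the control.

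**Working it through.** No figure in the documents bears on this point, so there is none to reproduce. The check has two parts: what the planned tests cover, and how they behave in simulation.

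**Coverage.** The fallback paragraph names six outcomes: STICSA somatic and cognitive, PANAS positive and negative, SAM valence and arousal. I assume that the MANCOVA uses the same six and that the variance tests are run on their changes. A 6 × 6 covariance matrix has 6 × 7 / 2 = 21 distinct elements.
- 6 variances: covered by the planned homogeneity-of-variances tests.
- 15 covariances: covered by no planned test.
- Covariate-by-condition slopes: covered by no planned test. The Protocol's rationale for measuring music preference gives a reason to expect a slope in the two arms with music and not in the two without.

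**Simulation inputs.**
- From the Protocol: 318 participants, four arms. 318 / 4 = 79.5, so arms of 80, 80, 79 and 79, assuming equal allocation (no ratio is stated).
- Assumed: Box's M with the chi-square approximation, alpha 0.05, two to five covariates, outcome correlation 0.3, 2,000 runs per setting.

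**Formula.** With p variables, k arms, arm sizes n_i, total N, arm covariance matrices S_i and pooled matrix S_p:
- M = (N − k) ln|S_p| − Σ (n_i − 1) ln|S_i|
- C = [Σ 1/(n_i − 1) − 1/(N − k)] × (2p² + 3p − 1) / [6(p + 1)(k − 1)]
- (1 − C)M is referred to chi-square with p(p + 1)(k − 1)/2 degrees of freedom.

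For the six outcomes, the degrees of freedom are 6 × 7 × 3 / 2 = 63 and C = (2/79 + 2/78 − 1/314) × 89/126 = 0.034.

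**Planned test, on the covariates (identically distributed in every arm).**
- Normal covariates: rejects about 5%, whether the outcome covariance matrices are equal or not.
- Skewed (gamma, shape 4) or heavy-tailed (t, 5 df) covariates: rejects about 24% to 62% across two to five covariates. With five covariates it is about 28% for gamma and 60% for t.
- The rate depends on the assumed shape. A multivariate t (5 df) with correlation 0.3 gives 57% with two covariates and 92% with five. At alpha 0.001 these fall to 22% and 64%.

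**Tests on the six outcomes, about 80 per arm.** The Levene column is the chance that at least one of six tests rejects after Bonferroni adjustment.

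| True state | Box's M on outcomes | Levene on outcomes |
|---|---|---|
| Equal matrices | 5% | 4% |
| One arm, correlation 0.6 instead of 0.3 | 96% | 4–5% |
| One arm, SD × 1.5 | 100% | 100% |

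Without the adjustment, at least one Levene test rejects in about 23% of trials in both of the first two rows, so it still does not distinguish them. At the Protocol's minimum of 45 per arm, Box's M on the outcomes detects the correlation difference 63% of the time at alpha 0.05 and 14% at alpha 0.001.

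**The case against.** Four arguments have weight.

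- **The variance tests already protect the outcomes.** A reader might infer that the gate would pass any MANCOVA whose covariance assumption fails, including one with a larger SD in one arm. The documents do not support that: the same SAP sentence tests outcome variances, and those tests catch an SD ratio of 1.5 almost always. Only correlation differences and slopes are left uncovered.
- **The omnibus test is robust here.** With near-equal arms and Pillai's trace (both assumed), its simulated null rejection rate stayed between about 5% and 7% with one arm's SD at 1.5 times the others, with one arm's correlation at 0.6, or with a slope of 0.4 in two arms only. Unequal slopes are effect modification; they do not invalidate the randomised comparison. It would be wrong to infer that a MANCOVA reached through this gate is invalid.
- **This check is seldom decisive.** Shapiro-Wilk on coarse scores such as SAM may trigger the fallback whatever the covariance test shows. A reader might take the 24% to 62% as the share of trials sent to the wrong analysis. It is only the rejection rate of one pretest among several, under an assumed test, alpha and covariate shape. A diversion also leads to a prespecified analysis of the same outcomes.
- **The wording may be garbled**, with homogeneity of regression slopes intended. That check would also need the dependent variables, and the text does not state it.

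Differential dropout could make the covariates differ among completers, but a test on them would still not address the outcome assumption. All four arguments reduce the consequence. None makes the test informative about the assumption it is meant to check.

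**Conclusion.** The point stands as a minor correction. As written, one component of the decision rule tests the wrong variables. It has no ability to detect unequal outcome covariance matrices and can reject only by chance or through non-normal covariates. The real gap is confined to outcome correlations and covariate slopes.

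The practical harm is an uninformative gate on the choice of analysis, with the loss of two comparisons against pink noise if the fallback is triggered. I do not put a figure on net misrouting, because that depends on the other pretests and on details the SAP leaves open. The simulated rates rest on Box's M at 0.05, near-equal arms totalling 318, six outcomes, two to five covariates and the stated distributions. The statement that a test on pre-exposure covariates cannot check the outcome assumption rests on none of these.

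**What to change.** In the first paragraph of the SAP:

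1. Delete the covariance test on music preferences and personality type.
2. Assess covariance homogeneity by arm on the MANCOVA residuals of the STICSA, PANAS and SAM changes, naming the test and its alpha.
3. Add a check of covariate-by-condition slopes, music preference (STOMP) first.

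If the gate is dropped and one analysis is prespecified, keep items 2 and 3 as reported diagnostics and use Pillai's trace for the omnibus test.

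The cost is about one sentence of SAP wording. No new data are needed.
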